17.1 PROTECTION OF HUMAN SUBJECTS

The investigator agrees to conduct this study in accordance with the International Conference on Harmonization (ICH) principles of Good Clinical Practice and with the Declaration of Helsinki (1989). The investigator will conduct all aspects of this study in accordance with all national, state, and local laws of the applicable regulatory agencies.

Most patients will be children, adolescents, and young adults because of the nature of these tumors. Patients of both sexes and all ethnic backgrounds are eligible for this study. Alternative treatments are available and will be discussed with patient or legal guardian. Patients are responsible for the costs of physician visits and usual laboratory tests, hospitalizations, and outpatient care. If there is an injury as a result of this research study,

emergency care, hospitalization, and outpatient care will be made available by Memorial Hospital and billed to the patient as part of the medical expenses. No money will be provided by Memorial Hospital as compensation for research-related injury.

17.2 Privacy

MSKCC's Privacy Office may allow the use and disclosure of protected health information pursuant to a completed and signed Research Authorization form. The use and disclosure of protected health information will be limited to the individuals described in the Research Authorization form. A Research Authorization form must be completed by the Principal Investigator and approved by the IRB and Privacy Board.

17.3 Serious Adverse Event (SAE) Reporting

Any SAE must be reported to the IRB as soon as possible but no later than 5 calendar days. The IRB requires a Clinical Research Database (CRDB) AE report to be submitted electronically to the SAE Office at [contact]. The report should contain the following information:

Fields populated from the CRDB:

- Subject's name (generate the report with only initials if it will be sent outside of MSKCC)
- Medical record number
- Disease/histology (if applicable)
- Protocol number and title

Data needing to be entered:

- The date the adverse event occurred
- The adverse event
- Relationship of the adverse event to the treatment (drug, device, or intervention)
- If the AE was expected
- The severity of the AE
- The intervention
- Detailed text that includes the following information:
 - A explanation of how the AE was handled
 - A description of the subject's condition
 - Indication if the subject remains on the study
 - If an amendment will need to be made to the protocol and/or consent form

The PI's signature and the date it was signed are required on the completed report.

For IND/IDE protocols:

The CRDB AE report should be completed as above and the FDA assigned IND/IDE number written at the top of the report. If appropriate, the report will be forwarded to the FDA by the SAE staff through the IND Office.

All SAEs **must** be entered into the CRDB SAE form page.

SAEs are defined as grade 4 toxicities other than fatigue, weight loss or weight gain, anorexia, nausea, anxiety, constipation, urinary retention from opioid analgesics, somnolence/hallucinations/ disorientation/confusion/ agitation/anxiety from anti-histamine and opioid premedications, hypomagnesemia, fever, rash, dry skin from accutane, urticaria from 3F8 or GMCSF, myelosuppression from the combination of 3F8 and GM-CSF and pain and transient hypoxia from opioids, breathholding, with or without transient oxygen requirement. Preexisting conditions e.g. hearing loss, hyperbilirubinemia or elevated LFTs from TPN, alopecia are not counted as SAEs.

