11.1 TOXICITIES/SIDE EFFECTS

11.2 Toxicities are graded by the Common Toxicity Criteria (Version 2.0) developed by the National Cancer Institute (NCI) of the USA.

11.3 3F8: Reversible side-effects include pain, paresthesia, hypertension, hypotension, tachycardia, urticaria, fever, nausea, emesis, and rarely, diarrhea, serum sickness, hyponatremia, somnolence and posterior reversible encephalopathy syndrome (PRES). Other potential side-effects that may occur are bronchospasm, anaphylaxis, peripheral neuropathy, impaired accommodation of the eye, and poor reactivity of pupils to light.

11.4 GM-CSF: Common side-effects include bone pain, flushing, local reaction at site of injection, leukopenia shortly after injection, and decrease in platelet count.⁹⁸ Rare side-effects (predominantly in adults) include allergic reactions, weight gain, pleural or pericardial effusion, pericardial embolism, thrombosis, and difficulty breathing after first injection.

11.5 Isotretinoin: Dry skin, cheilitis, dry eyes, hypercalcemia, pseudotumor cerebri, hepatotoxicity, teratogenic effect on fetus, depression, suicidal ideation.

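### Section 17.3 ties the 5-day SAE report to grade 4 toxicities minus exceptions, so as written some deaths and serious events do not trigger it

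*Combined protocol and SAP*

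**What the plan says.** Section 17.3 sets the duty: "Any SAE must be reported to the IRB as soon as possible but no later than 5 calendar days". It then says which events carry that duty: "SAEs are defined as grade 4 toxicities other than fatigue". The exceptions continue through weight change, anorexia, nausea, anxiety, constipation, effects of opioid and antihistamine premedication, fever, rash, dry skin from isotretinoin and urticaria from 3F8 or GM-CSF, and end with "myelosuppression from the combination of 3F8 and GM-CSF and pain and transient hypoxia from opioids, breathholding, with or without transient oxygen requirement". A last sentence removes a further class: "Preexisting conditions e.g. hearing loss, hyperbilirubinemia or elevated LFTs from TPN, alopecia are not counted as SAEs".

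For protocols under an IND, the same section has staff complete the same report form, add the IND number and, where appropriate, have it forwarded to the FDA. Section 5.2 shows that 3F8 is given under an IND.

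Four other places bear on the point:

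- Section 11.2 grades toxicity by the NCI Common Toxicity Criteria, version 2.0. The scale is not reproduced.
- Section 13.4 removes a patient for a grade 4 toxicity that is life-threatening and clearly due to 3F8. Section 9.2 has a similar rule.
- Section 16.3 applies the institution's phase II monitoring procedures, including adverse event notification. It refers to an appendix for the details, and provides for tabulation of all adverse events and an annual report to the IRB.
- Section 17.1 commits the investigator to conduct the study "in accordance with the International Conference on Harmonization (ICH) principles of Good Clinical Practice" and with applicable law.

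**The concern.** A definition of a serious event decides which events are reported within days and which wait for a tabulation or an annual report. Here the definition rests on one toxicity grade. It does not say grade 4 or higher, and it does not mention death, hospital admission or disability. The exceptions apply at grade 4 and carry no condition that the event was not life-threatening.

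This is more than missing detail. The section states a specific rule, written for this trial (the exceptions name 3F8, GM-CSF and isotretinoin), and that rule leaves out events that one would expect an SAE rule to catch. What is at stake is how quickly the IRB and, through the IND route, the regulator hear of such events in a mainly paediatric population. No efficacy estimate, sample size or error rate is affected.

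**Working it through.** No arithmetic applies. The check is to run the kinds of event that matter through the rule as written, and then to look for any other section that would catch them.

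**The rule.** An event is an SAE if (a) it is a toxicity, (b) it is grade 4, (c) it is not on the exception list, and (d) it is not a pre-existing condition. The 5-day report follows if all four hold.

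1. *A death.* Section 17.3 does not mention death. If the fatal event is recorded as a grade 4 toxicity and is not excepted, the report is triggered. If it is recorded in another way, or is not regarded as a toxicity at all (for example a death not attributed to treatment), condition (a) or (b) fails and there is no 5-day trigger.
2. *A serious event of another grade.* Condition (b) fails whatever the consequence for the patient. Section 11.3 lists posterior reversible encephalopathy syndrome and anaphylaxis as possible with 3F8 and assigns no grade to either. If such an event were graded below 4 and still led to admission, it would fall outside the rule. If it were graded 4 it would be inside, since neither is on the exception list. These examples are therefore conditional.
3. *An excepted grade 4 event that is life-threatening.* Urticaria from 3F8 is excepted without qualification, so condition (c) fails at grade 4. If that event were life-threatening and clearly due to 3F8, it would meet the removal rule in Section 13.4. The same event could then take a patient off study and still not count as an SAE. The two sections need to be reconciled.

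**Does another section fill the gap?**

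- Sections 9.2, 11 and 13 add no reporting criterion. Section 13.5 mentions a serious event report for patients removed because of adverse events, without saying what makes an event serious.
- Section 16.3 tabulates all adverse events and reports yearly to the IRB. Neither is a 5-day report. The institutional procedures that it invokes are in an appendix not available for this review.
- Section 17.1 gives a general commitment, with no criterion and no deadline.
- Section 17.3 does not defer to Section 16.3 or 17.1 for its definition.

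**IND route.** The report forwarded to the FDA is the form completed for the IRB. An event outside the definition prompts neither by this route.

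**The case against.** The strongest reply is that Section 17.3 does not stand alone. Section 16.3 says that the institutional procedures apply and will be followed, and Section 17.1 binds the investigator to GCP and to national, state and local law. Either may require prompt reporting of deaths and other serious events, and nothing in Section 17.3 forbids reporting more than it lists. This stands, and it limits the conclusion. A reader might infer that deaths on this trial would go unreported. The documents do not support that: the appendix is not available, the parallel obligations are real, and every adverse event is tabulated in any case. The reply does not repair Section 17.3, however. That section gives its own definition instead of pointing to the policy. If the policy is broader, the two conflict and staff need to know which governs.

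A second reply is that the toxicity scale is not reproduced, so the documents alone cannot settle how a death or a given reaction is graded. This also stands. It is why the case of a death is put as one not recorded as a grade 4 toxicity, and why the two reactions from Section 11.3 are only conditional examples. The gap itself does not depend on the scale, because the rule admits one grade and sets no criterion based on outcome.

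A third reply is that many exceptions are tied to a named cause and are expected effects of the regimen, so excluding them from expedited reports is sensible. That is fair as far as it goes. The difficulty is only that the exceptions are not limited to events that are neither fatal nor life-threatening.

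**Conclusion.** The point holds as a defect in the stated rule. As written, the 5-day IRB report and the IND route attach only to grade 4 toxicities outside the exception list. Deaths not recorded that way, serious events of other grades, and life-threatening events on the exception list do not trigger them.

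The size cannot be given. The documents contain no rate for any of these events, and the numbers of patients or cycles would measure exposure, not missed reports. The conclusion rests on a literal reading of Section 17.3 and on the absence of any further criterion in the sections available. If the institutional appendix has a broader definition, the practical consequence is smaller, but Section 17.3 would then contradict it and would still need correction. The change should be made. It concerns safety reporting only.

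**What to change.** Reword Section 17.3 so that the 5-day duty explicitly covers:

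- any death on study, from any cause;
- any life-threatening event;
- any event that causes or prolongs hospital admission, or causes lasting disability;
- any grade 4 toxicity, apart from the listed exceptions.

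State that the exceptions apply only to expected events that are neither fatal nor life-threatening. Reconcile the section with the removal rule in Section 13.4, the undefined serious event report in Section 13.5, the institutional procedures in Section 16.3 and the commitments in Section 17.1, and say which text governs if they differ.

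The cost is a protocol amendment to the wording and some additional expedited reports. No dose, schedule, endpoint or sample size changes.

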18.1 INFORMED CONSENT PROCEDURES

Before protocol-specified procedures are carried out, consenting professionals will explain full details of the protocol and study procedures as well as the risks involved to participants prior to their inclusion in the study. Participants will also be informed that they are free to withdraw from the study at any time. All participants must sign an IRB/PB-approved consent form indicating their consent to participate. This consent form meets the requirements of the Code of Federal Regulations and the Institutional Review Board/Privacy Board of this Center. The consent form will include the following:

1. The nature and objectives, potential risks and benefits of the intended study.
2. The length of study and the likely follow-up required.
3. Alternatives to the proposed study. (This will include available standard and investigational therapies. In addition, patients will be offered an option of supportive care for therapeutic studies.)
4. The name of the investigator(s) responsible for the protocol.
5. The right of the participant to accept or refuse study interventions/interactions and to withdraw from participation at any time.

Before any protocol-specific procedures can be carried out, the consenting professional will fully explain the aspects of patient privacy concerning research specific information. In addition to signing the IRB Informed Consent, all patients must agree to the Research Authorization component of the informed consent form.

Each participant and consenting professional will sign the consent form. The participant must receive a copy of the signed informed consent form.

